11.13 Monitoring and Management of Abnormal Electrocardiograms

If a CS ECG abnormality occurs that was not present at baseline (Screening) and the investigator determines that the abnormality is related to IP, the abnormality will be discussed with the medical monitor. The ECG abnormality will be monitored and evaluated with additional tests (if necessary) until the underlying cause is determined or the event is brought to an acceptable resolution. Additional clinical and laboratory information will be collected and carefully documented in order to better characterize the ECG abnormality and rule out alternative causes. ECG findings determined to be a CS change from baseline should be reported as an AE regardless of causality.

Unscheduled ECG assessments will be completed at the discretion of the investigator.

11.14 Intravenous Access Considerations

IP dosing will be administered through IV infusion. Peripheral venous access (IV catheter that empties into a peripheral vein in the arms, hands, legs, or feet) is the preferred route of IP administration for this study.

A CVA (IV catheter that empties into a large central vein) will be considered on a case-by-case basis for patients who have difficulty with peripheral venous access. A TICVAD port is the preferred option of CVA, if necessary, for this study. The sponsor will decide whether or not to approve this option after discussions with the investigator and medical monitor have ensured mutual agreement that CVA will still maintain a positive benefit/risk ratio for the patient in this study. Before final decision, NS Pharma, Inc. will obtain documentation from the investigator that the consulting surgeon who will place the port holds hospital privileges as a board eligible/board certified surgeon. The decision, rationale, and conclusion regarding the

maintained positive benefit/risk ratio will be detailed in writing and sent to the requesting site.
CVA should not be implemented without sponsor approval.

An alternative method of CVA may only be considered in the case of a documented contraindication to the placement of a TICVAD.

11.15 Data and Safety Monitoring Board

It is the responsibility of the DSMB to review data quality, relevant safety data, and AEs for all patients enrolled in the study and to make recommendations to the study chair, medical monitor, and sponsor regarding the ongoing conduct and monitoring of the study. Details are provided in the DSMB charter.

12 PLANNED STATISTICAL METHODS

12.1 General Considerations

The statistical analyses described in this section will be performed as further outlined in the Statistical Analysis Plan (SAP), which will be finalized prior to database lock. The SAP will supersede the protocol if there are any differences between the 2 documents in the plans for data analysis and the differences will be noted in the SAP. The SAP will be included as an appendix in the Clinical Study Report for this protocol. The data will be hosted and processed by Medpace, Inc. Statistical analyses will be performed using SAS[®] 9.4 or higher and R 4.05 or higher.

All measurements will be analyzed based upon the type of distribution, and descriptive statistics will be presented by time point, as appropriate.

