2.2.2 Current Natural History, Disease Management, and Treatment Recommendations

The Cooperative International Neuromuscular Research Group (CINRG) conducted the largest prospective multicenter natural history study to date in DMD, the CINRG DMD Natural History Study (DNHS) (McDonald et al, 2013; Henricson et al, 2013; McDonald et al, 2018). The study included >400 boys and men with DMD, with variable amounts of longitudinal follow-up over the course of a decade (2006 to 2016). The study had annual follow-up visits that included timed function tests, muscle strength, functional assessment questionnaires, pulmonary function tests, and quality of life assessments.

Since there is currently no cure for DMD, the goal of care is to provide the best quality of life through all stages of the disease. To date, treatments focus on optimizing strength and function through the use of pharmacological interventions, physical therapy, and assistive and adaptive devices.

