5 INVESTIGATIONAL PLAN

5.1 Overall Study Design and Plan

This is a Phase 2, open-label study with DMD boys receiving 80 mg/kg viltolarsen administered IV at weekly doses in ambulant and non-ambulant boys ≥ 8 years of age with DMD over a 48-week Treatment Period. See [Section 1.1](#) for study schema.

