12.6 Efficacy Assessments

12.6.1 Secondary Objective

The secondary objective is to compare the efficacy of viltolarsen administered IV at weekly doses of 80 mg/kg over a 48-week Treatment Period versus natural history controls in ambulant and non-ambulant boys ≥ 8 years of age with DMD for the following endpoints: absolute and percent predicted PEF, FVC, and FEV1, Brooke and Vignos functional scales, and the NSAA. The PUL and hand-held dynamometry will be described and the change over time estimated for the viltolarsen-treated group only.

In addition to the comparison methods described below, all outcomes for both the viltolarsen-treated and historical control groups will be summarized and tabulated at each time point assessed. Time points in the historical control will match those of the viltolarsen-treated group within pre-defined tolerances. Outcomes at baseline will be compared between viltolarsen and control groups using methods appropriate for the distribution of each outcome.

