12.6.1.8 Analyses Comparing NS-065/NCNP-01 Patients to Historical Controls

A matched data set from the CINRG DNHS data will be created. The purpose of the matching is to create a group data set that corresponds in characteristics to the patients in this study. The CINRG DNHS data set includes patients from 2 years old to over 30 years old, some of whom have been followed for close to a decade. Therefore, it is important to create a comparator group which will allow valid group comparisons. No patient-to-patient matched analysis is proposed. The sole purpose of the matching is to create a historical control group which is comparable in its basic characteristics to the study patient group. The final CINRG DNHS data set is expected to have between 16 and 32 patients included with time intervals of evaluations between 6 and 15 months.

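### With open-label treatment and controls whose outcomes already exist, a database-lock deadline does not keep control selection, visit windows and three conditional model terms apart from the results

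*Combined protocol and SAP*

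**What the plan says.** Section 12.1 says the analyses will be detailed in a SAP "which will be finalized prior to database lock", and adds: "The SAP will supersede the protocol if there are any differences between the 2 documents". Differences are to be noted in the SAP, which will be appended to the study report. Section 5.1 describes the design: "This is a Phase 2, open-label study with DMD boys receiving 80 mg/kg viltolarsen". Section 7.4 states that blinding does not apply.

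On the controls, Section 12.6.1.8 says: "A matched data set from the CINRG DNHS data will be created". The aim is a group comparable to the study patients in basic characteristics. The resulting set is "expected to have between 16 and 32 patients included with time intervals of evaluations between 6 and 15 months". No matching variables, calipers, algorithm, date or responsible party are named. Section 2.2.2 describes the source as more than 400 boys and men followed between 2006 and 2016; the protocol is first dated January 2021.

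Section 12.6.1 says control time points will be aligned with study visits within tolerances set beforehand, but gives no values. It also says: "Outcomes at baseline will be compared between viltolarsen and control groups using methods appropriate for the distribution of each outcome".

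For lung function (Sections 12.6.1.1 to 12.6.1.3) and the Brooke and Vignos scales (12.6.1.4), the model is a repeated-measures mixed model with a random term per patient and with age and baseline value as covariates. The time-by-treatment interaction enters only when judged appropriate, the steroid covariate only when judged necessary, and the random slope after its predictive value has been assessed. Section 12.6.1.7 (NSAA) repeats the steroid condition.

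**The concern.** Finalising a SAP before lock works in a blinded randomised trial because nobody can link outcomes to treatment until then. Here neither side of the comparison is hidden. Every study patient is known to be on viltolarsen, and efficacy data accrue at Weeks 13, 25, 37 and 49, before lock. The control outcomes were on file before the protocol was written. A choice made the day before lock can therefore be made, even without intent, with both sets of results in view.

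The open choices are influential ones: who the controls are, which of their visits count, and whether the model contains the interaction. In a model of change over time the interaction normally carries the treatment contrast, so leaving it optional leaves open what is being estimated.

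At stake is the only controlled efficacy comparison in the study. The primary safety objective does not depend on it.

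**Working it through.** **The plan's own figure.** The only design calculation is the safety one in Section 12.2: with 20 patients and a 15% incidence, the chance of at least one event is 1 − 0.85^20 = 0.961, which agrees with the stated 95% or more. It is not in dispute. No significance level, power, effect size or SD is given for the historical comparison, so there is no plan figure to correct.

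**What is fixed and what is open.**

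| Item | Status | Section |
|---|---|---|
| Control source (DNHS) | Fixed | 12.6.1.8 |
| Mixed-model class; age and baseline covariates | Fixed | 12.6.1.1, 12.6.1.4, 12.6.1.7 |
| Group-level analysis, not paired | Fixed | 12.6.1.8 |
| Control eligibility, matching variables, algorithm | Open | 12.6.1.8 |
| Visit tolerances | To be set beforehand, values not given | 12.6.1 |
| Interaction, random slope | Conditional, no rule | 12.6.1.1, 12.6.1.4 |
| Steroid covariate | Conditional, no rule | 12.6.1.1, 12.6.1.4, 12.6.1.7 |

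Where all three conditional terms apply, they allow 2 × 2 × 2 = 8 model forms per endpoint, before any choice of control set.

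**What separates the choices from the outcomes.** Section 12.1 gives lock as the outer limit. Section 12.6.1.8 does not say that the control list must be in the SAP or complete by lock. Section 12.8 plans no interim analyses, but that is not a rule about who may see accumulating open-label data. No other restriction on access to efficacy data before lock was found.

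**Illustration of size.** Inputs from the documents: 20 treated patients; 16 or 32 controls. Assumed, because the documents give no values: independent normal outcomes with equal SD and no true effect; a nominal one-sided 2.5% level in favour of treatment; the eligible pool; and K, the number of candidate control sets considered. For each simulated trial, draw K random control sets of size m from one pool and compute for each

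t = (treated mean − control mean) / [pooled SD × √(1/20 + 1/m)].

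Take the largest t and compare it with the 97.5th percentile of t on 18 + m degrees of freedom. Results, rounded to the nearest half point for small pools and whole point for larger ones:

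| Controls used, from pool of | Best of 3 | Best of 5 | Best of 10 |
|---|---|---|---|
| 32 from 36 | 3.5% | 4% | 5% |
| 32 from 40 | 4% | 4.5-5% | 6% |
| 16 from 20 | 4-4.5% | 5-5.5% | 6.5-7% |
| 16 or 32 from 60 or 100 | 5-6% | 6-9% | 8-14% |

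With one set fixed in advance (K = 1) the error stays at about 2.5% and the bias is about zero. At 6,000 runs, simulation error near 6% is √(0.06 × 0.94 / 6000) = 0.003, or 0.3 points.

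The same selection shifts the estimated difference, whatever significance level is used. In pools of 60 to 100 the shift is about 0.1-0.2 SD for the best of 3 sets, 0.14-0.27 SD for 5 and 0.2-0.35 SD for 10. It is smaller in small pools. The choice of model form is not simulated.

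**The case against.** The strongest reply is that much is already settled. Source, model class, main covariates and a group-level analysis are fixed, and visit tolerances are to be set beforehand. Departures from the protocol must be noted in a SAP that is appended to the report. Lock is only an outer limit: no separate SAP text is in the document supplied, so the rules may in fact have been fixed early. The comparison is secondary, with no declared test or success criterion, and Section 2.1.3 openly acknowledges how hard an external control is to interpret.

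Most of this stands, and it confines the point to the open items. It does not remove it. Noting differences discloses a departure, but filling a gap on which the protocol is silent is not a departure. An early SAP would be good practice, but the protocol does not require one.

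Three stronger readings are tempting and not supported:

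- A reader might infer that eligible controls are being discarded without reason because individual matching is not planned. Section 12.6.1.8 rules out only a paired analysis. Selecting a comparable group can itself require leaving patients out.
- A reader might take 16 to 32 as a quota, or as one to two controls per patient for a trial of 16 rather than 20. The text calls it an expectation and states no ratio. Restricting a cohort aged 2 to over 30 to comparable boys could plausibly leave that many.
- A reader might infer a large reservoir from the more than 400 DNHS patients. The number eligible is not given, so neither the upper error figures nor a gain in precision from a larger control group can be claimed as fact.

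**Conclusion.** The point holds in limited form. The stated deadline does not separate three things from outcomes that can be seen beforehand: the control selection rules, the visit-tolerance values and the three conditional model terms. It would be too strong to say that the whole comparison model is open, or that controls have been or will be chosen for their results; nothing in the documents says so.

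Under the assumptions above, a nominal 2.5% error becomes about 3.5-6% with the best of 3 sets, 4-9% with 5 and 5-14% with 10. The low ends belong to pools barely larger than the control set, the high ends to pools of 60 to 100. These figures show direction and rough scale; they do not predict this trial's error rate. The change is a cheap improvement that should be made, because the separation cannot be restored once outcomes have been compared.

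**What to change.** In Sections 12.1 and 12.6.1.8, state that the following will be fixed and dated before any post-baseline efficacy data are compared with controls:

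- the DNHS eligibility criteria;
- the matching variables (for example age, ambulatory status, glucocorticoid use and baseline value);
- the visit windows, with values;
- the full comparison model, stating whether the interaction, steroid covariate and random slope are in it.

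Select the controls from a DNHS extract that holds baseline data only. Archive the selected list, and merge follow-up outcomes only afterwards. Report balance by standardised differences, which, unlike a test of baseline values, do not depend on group size for their interpretation.

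The cost is protocol and SAP wording and an extract split into baseline and follow-up files. The downside is less freedom to refine the control set later; any later refinement can be reported as a labelled sensitivity analysis.

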12.2 Determination of Sample Size

Assuming a sample size of 20, at least 1 adverse drug reaction with an incidence of 15% may be detected at a probability of $\geq 95\%$ for the safety profile, which is the primary outcome. Based on this, it was decided that 20 patients should be enrolled to confirm safety. A minimum of 8 ambulant patients will be enrolled.

12.3 Analysis Populations

The Safety Population will consist of all patients who received at least 1 dose of IP. This will be the primary analysis population for the evaluation of safety.

The modified Intent-to-Treat Population will consist of all patients who received at least 1 dose of IP and have a baseline assessment and at least 1 post-baseline efficacy assessment. This will be the analysis population for the evaluation of efficacy.

12.4 Demographics and Baseline Characteristics

Summaries of patient demographics (age, race, ethnicity, and dominant hand), baseline safety characteristics (anthropometrics, vital signs, physical examination, hematology, chemistry, urinalysis, ECG, echocardiogram, and antibodies), and baseline efficacy parameters will be done.

12.5 Primary Safety Endpoints

12.5.1 Primary Objective

Safety analyses will be performed using the Safety Population. TEAEs will be summarized by system organ class and preferred term (using the Medical Dictionary for Regulatory Activities [MedDRA]), by relationship to IP, and by intensity (CTCAE grade).

12.5.2 Anthropometrics, Vital Signs, Laboratory Assessments, Electrocardiogram, and Echocardiogram

Anthropometrics, vital signs, hematology, chemistry, urinalysis, ECG, and echocardiogram results will be summarized over time using descriptive statistics for continuous outcomes. Actual values and change from Day 1 will be presented. Further, all laboratory abnormalities will be listed.

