- k. For each visit that includes an IP administration, vital signs will be performed at predose, as well as 1 hour (up to 20 minutes following completion of the infusion) and 2 hours (± 20 minutes) after initiation of infusion. If a clinically significant change from predose is observed at 2 hours after initiation of infusion, the parameter will be measured again at 6 hours (± 20 minutes) after initiation of infusion. Vital signs will be measured prior to any blood collection scheduled at the same time point and will include systolic and diastolic blood pressure, heart rate, respiratory rate, and temperature (modality for determining temperature should be consistent for each patient at all assessment time points throughout the study).
- l. Physical and neurological examinations will include an assessment of the following: general appearance, HEENT, skin, lymph nodes, heart, including rhythm, heart sounds, and presence of cardiac abnormalities, lungs, abdomen, extremities/joints, nervous system, and any additional assessments necessary to establish baseline status or evaluate symptoms or adverse experiences as detailed in [Section 9.10](#).
- m. ECGs will be performed with the patient having rested for at least 5 minutes, and the patient should remain in the supine or semi-recumbent position. A consistent position should be maintained for each individual patient.
- n. Renal ultrasound will include imaging of the kidneys, ureters, and bladder.
- o. Any blood sampling that occurs during the IP infusion should be collected from the opposite arm. Post-infusion PK blood samples should not be drawn from the cannula that was used for the infusion. These samples can be drawn from the arm opposite the infusion or can be from a separate access point in the same arm as the infusion.
- p. Refer to [Table 3](#) for additional details on the clinical laboratory tests, including the laboratory analytes that will be measured for hematology, serum chemistry, and urinalysis.
- q. Patients will collect a first morning void urine sample on the date of the specified visit and bring it to the site. Analysis of the sample will include urine dipstick protein to be performed at the site. An aliquot will also be sent to the central laboratory for urinalysis. Refer to [Section 11.12.1](#) for details on monitoring of renal function and urine analyses.
- r. First morning void urine sample collection and dipstick protein are not required at screening.

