- s. To be performed on a predose urine sample collected on-site.
- t. To be performed on a urine sample collected within 5 hours after completion of infusion.
- u. To include hepatitis B antigen, hepatitis C antibody, and HIV antibody.
- v. To be collected predose and to be performed on serum blood samples.
- w. PK blood samples will be collected predose (within 60 minutes prior to infusion) and 2 hours (± 20 minutes) after initiation of infusion on Day 1 and at Week 13.
- x. Function and strength tests will include the following: Brooke and Vignos scales, PUL, NSAA, and hand-held dynamometer.
- y. PODCI and PARS III Questionnaire.
- z. ActiGraph GT9x will be provided at Screening; 10 hour daytime + full nighttime wear for full study period.
- aa. IP infusion will be administered every week within a ± 3 -day window. A minimum of 3 days (72 hours) should elapse between infusions.
- bb. The chest X-ray will include images of the heart, lungs, airways, blood vessels, and the bones of the spine and chest.

Table 2. Schedule of Study Assessments for Treatment Phase from Week 25 to End of Treatment Phase

Assessment ^a	Treatment Phase (Week 25 to Week 48) ^b ±3 days for each weekly visit														End-of-Treatment Phase		
	25	26 to 28	29	30 to 32	33	34 to 36	37	38 to 40	41	42 to 44	45	46	47	48	49	Follow-up Telephone Call ^c 30 days (±3 days) postdose	ET
General Procedures																	
Medical history ^d	X	X	X	X	X	X	X	X	X	X	X	X	X	X	X	X	X
Height ^e and weight ^f	X						X								X		X
Vital signs ^g	X	X	X	X	X	X	X	X	X	X	X	X	X	X	X		X
Physical and neurological examination ^h	X						X								X		X
12-lead ECG ⁱ	X						X								X		X
Renal ultrasound ^j	X														X		X
Echocardiogram ^k	X														X		X
Laboratory Assessments^l																	
Hematology ^m	X						X								X		X
Chemistry ^m	X						X								X		X
First morning void urinalysis ^{m,n}	X		X		X		X		X		X				X		X
Urine cytology ^o	X						X								X		X
Postdose urinalysis ^{m,p}	X						X										
Anti-dystrophin antibody ^q	X						X								X		
Anti-viltolarsen antibody ^q	X						X								X		
Pharmacokinetic Assessment																	
PK (blood) ^{l,r}	X						X								X		

Assessment ^a	Treatment Phase (Week 25 to Week 48) ^b ±3 days for each weekly visit														End-of-Treatment Phase		
	25	26 to 28	29	30 to 32	33	34 to 36	37	38 to 40	41	42 to 44	45	46	47	48	49	Follow-up Telephone Call ^c 30 days (±3 days) postdose	ET
Other Assessments																	

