If serum cystatin C $\geq 1.5 \times$ baseline, or if serum creatinine $\geq 2 \times$ baseline and ≥ 0.3 mg/dL, the test will be repeated within 1 week of the results. Refer to Section 11.12.1 for additional details on monitoring of renal function and urine analyses.

Samples will be collected by a trained member of the study team unless otherwise noted. All blood and urine samples will be sent to the designated central laboratory for testing unless otherwise noted. The urine cytology samples will be collected predose at the site and sent to a local laboratory for analysis. The procedures for the collection, handling, and shipping of central laboratory samples will be specified in the Laboratory Manual. Clinical laboratory tests are listed in Table 3.

Table 3. Clinical Laboratory Tests

Hematology, Chemistry, Urinalysis (Screening, First Morning Void, and Postdose), 24-Hour Urine Analysis, and Urine Cytology – Safety Labs

- Hematology
 - Red blood cell count
 - Hemoglobin
 - Hematocrit
 - Reticulocyte count
 - Mean corpuscular volume
 - Mean corpuscular hemoglobin
 - Mean corpuscular hemoglobin concentration
 - WBC
 - White blood cell differential
 - Platelet count
 - Fibrinogen
 - Activated partial thromboplastin time

-
- Prothrombin international normalization ratio
 - Blood Chemistry
 - Sodium
 - Potassium
 - Chloride
 - Calcium
 - Inorganic phosphorus
 - BUN
 - Creatinine
 - Cystatin C
 - Aspartate aminotransferase
 - Alanine aminotransferase
 - Gamma-glutamyl transferase
 - Alkaline phosphatase
 - Haptoglobin
 - Lactate dehydrogenase/lactate dehydrogenase isozyme
 - Creatine kinase
 - Total bilirubin (direct/indirect)
 - Total protein
 - Albumin
 - Albumin to globulin ratio
 - Total cholesterol
 - Triglyceride
 - Blood glucose
 - C-reactive protein
 - Urinalysis (Screening, First Morning Void, and Postdose)
 - Glucose
 - Blood
 - Urobilinogen
 - Specific gravity
 - Osmolality
 - Urinary sediment (erythrocytes, white blood cells, casts, epithelium, crystals)
 - Protein (benzethonium chloride method)
 - Microalbumin
 - N-acetyl-beta-D-glucosaminidase
 - α 1-microglobulin
 - β 2-microglobulin
 - Creatinine
 - Protein to creatinine ratio
 - Protein osmolality ratio
 - Dipstick protein (to be performed by the site on the first morning void urine samples)
 - 24-Hour Urine Analysis
 - Protein (benzethonium chloride method)
 - Creatinine
-

- Urine cytology

BUN = blood urea nitrogen; WBC = white blood cell count.

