10.1.1 Screening Visit (-28 to -8 Days)

The ICF/Assent Form must be obtained prior to any study-related procedures being conducted. Screening will include assessments to confirm eligibility (review of inclusion/exclusion criteria and review to confirm the DMD diagnosis and appropriate mutations).

Screening activities:

- Informed consent/assent
- Review of inclusion/exclusion criteria
- Confirm DMD diagnosis
- DMD genetic test
- Demographics
- Medical history
- Height and weight
- Vital signs
- Physical and neurological examination
- 12-lead ECG
- Renal ultrasound
- Echocardiogram
- Antigen and antibody testing: hepatitis B antigen, hepatitis C virus antibody, and HIV antibody
- Hematology
- Chemistry
- Urinalysis (random urine)

- Respiratory assessments
 - FVC
 - FEV1
 - PEF
 - PCF
- Function and strength
 - NSAA
 - Vignos scale
 - Hand-held dynamometer
 - Brooke scale
 - PUL
- Patient reported outcomes
 - PODCI
 - PARS III Questionnaire
- AE review
- Provision of the ActiGraph GT9x and wear protocol

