10.2.1 Day 1 Dosing Visit (First Infusion)

The following assessments will occur:

- Medical history (any updates will be recorded)
- Height and weight
- Vital signs (predose, 1 hour [up to 20 minutes following completion of the infusion] and 2 hours [\pm 20 minutes] after initiation of infusion)
- Physical and neurological examination
- 12-lead ECG

- Hematology
- Chemistry
- Postdose urinalysis (utilizing a urine sample collected within 5 hours after completion of the infusion)
- Anti-dystrophin antibody (predose)
- Anti-viltolarsen antibody (predose)
- PK blood sample (predose [within 60 minutes prior to infusion] and 2 hours [\pm 20 minutes] after initiation of infusion)
- IP administration
- Respiratory assessments
 - FVC
 - FEV1
 - PEF
 - PCF
- AE review
- Data upload from ActiGraph GT9x

10.2.2 Week 2

The following assessments will occur:

- Medical history (any updates will be recorded)
- Vital signs (predose, 1 hour [up to 20 minutes following completion of the infusion] and 2 hours [\pm 20 minutes] after initiation of infusion)
- IP administration
- AE review
- Data upload from ActiGraph GT9x

10.2.3 Week 3

The following assessments will occur:

- Medical history (any updates will be recorded)

- Vital signs (predose, 1 hour [up to 20 minutes following completion of the infusion] and 2 hours [\pm 20 minutes] after initiation of infusion)
- Hematology
- Chemistry
- First morning void urinalysis

Note: Analysis of the first morning void urine sample will include urine dipstick protein to be performed at the site.

- IP administration
- AE review
- Data upload from ActiGraph GT9x

10.2.4 Week 4

The following assessments will occur:

- Medical history (any updates will be recorded)
- Vital signs (predose, 1 hour [up to 20 minutes following completion of the infusion] and 2 hours [\pm 20 minutes] after initiation of infusion)
- IP administration
- AE review
- Data upload from ActiGraph GT9x

10.2.5 Week 5

The following assessments will occur:

- Medical history (any updates will be recorded)
- Vital signs (predose, 1 hour [up to 20 minutes following completion of the infusion] and 2 hours [\pm 20 minutes] after initiation of infusion)
- Physical and neurological examination
- Hematology
- Chemistry

- First morning void urinalysis

Note: Analysis of the first morning void urine sample will include urine dipstick protein to be performed at the site.

- IP administration
- AE review
- Data upload from ActiGraph GT9x

10.2.6 Weeks 6 to 8

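### Section 12.5.2 takes safety changes from Day 1, but no echocardiogram and no first morning void is scheduled on Day 1

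*Combined protocol and SAP*

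**What the plan says.** Section 12.5.2 covers anthropometrics, vital signs, hematology, chemistry, urinalysis, ECG and echocardiogram. It plans descriptive summaries over time and sets one reference for all of them: "Actual values and change from Day 1 will be presented". No group is excepted.

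The schedule in Section 1.2 and the visit lists in Section 10 place the relevant assessments as follows.

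- Echocardiogram: at Screening (Section 10.1.1), then Weeks 25 and 49. Neither the Day 1 column of Table 1 nor the Day 1 list in Section 10.2.1 includes it.
- First morning void: at the Pre-Infusion Visit (Section 10.1.2), then from Week 3 onward. Table 1, footnote r, states: "First morning void urine sample collection and dipstick protein are not required at screening". The Screening urine is a random sample (Section 10.1.1). No first morning void is scheduled on Day 1.
- Day 1 urine: post-dose only. Table 1, footnote t, reads: "To be performed on a urine sample collected within 5 hours after completion of infusion".

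Table 3 in Section 9.15.1 names Screening, first-morning-void and post-dose urine as distinct kinds of urinalysis. Section 12.4 plans baseline summaries of both urinalysis and echocardiogram but does not define baseline. On precedence, Section 12.1 says: "The SAP will supersede the protocol if there are any differences between the 2 documents in the plans for data analysis".

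**The concern.** A programmer who follows Section 12.5.2 literally has nothing to subtract for the echocardiogram. For urinalysis the only Day 1 value is a post-infusion sample. The first-morning-void changes must then either be left empty or be taken against a sample of another type, collected after the first exposure. The second course is the worse one, because it would produce a table that looks complete.

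Urinalysis and echocardiogram are both listed as primary endpoints in Section 3, and Section 2.3.2.3 names the kidney as the primary target organ in the animal studies. The study has one treated arm and no concurrent control for safety, so change within the patient is one of the main ways a reader would judge these measures.

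**Working it through.** The plan gives no figure on this point. The check is a count of scheduled visits from Tables 1 and 2, compared with the visit lists in Sections 10.1.1 to 10.3.1. Early-termination visits are left out and full attendance is assumed. A change counts as computable only if Day 1 has a value of the same kind.

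| Series | Scheduled before first infusion | Day 1 value | Later scheduled visits | Computable from Day 1 |
|---|---|---|---|---|
| Echocardiogram | Screening | none | Weeks 25, 49 (2) | 0 of 2 |
| First morning void | Pre-Infusion | none | Weeks 3, 5, 9, 13, 17, 21 (6, Table 1) and 25, 29, 33, 37, 41, 45, 49 (7, Table 2) (13) | 0 of 13 |
| Post-dose urine | none | yes, after the infusion | Weeks 13, 25, 37 (3) | 3 of 3, from a post-exposure value |

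1. Later values in these three series: 2 + 13 + 3 = 18 per patient.
2. Without a Day 1 value of the same kind: 2 + 13 = 15 per patient.
3. At the planned 20 patients with full attendance: 20 × 15 = 300 (20 × 2 = 40 echocardiograms and 20 × 13 = 260 first morning voids).
4. With the last pre-infusion value of the same type as baseline, the Screening echocardiogram serves 2 of 2 and the Pre-Infusion void serves 13 of 13. All 15 become computable.

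The denominator of 18 covers only these three series. The other groups named in Section 12.5.2 do have Day 1 entries: hematology and chemistry (9 later scheduled visits), ECG (4 later scheduled visits), vital signs, and height and weight. They are not affected.

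The text was also searched for a convention that would let Day 1 stand for baseline. Section 12.5.2 does not say so, and Section 12.4 leaves the term open. Section 11.13 equates baseline with Screening for ECG abnormalities, although an ECG is also scheduled on Day 1. The protocol therefore has no single convention to fall back on.

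These counts measure computability, not bias. The documents do not allow the size or direction of a shift between a first morning void and a post-dose sample to be estimated.

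**The case against.** The strongest reply is that this is loose wording, not a fault in design or data. Pre-treatment values of the right kind are scheduled, Section 12.4 shows that the authors expected a baseline for both measures, and Day 1 may simply be shorthand for it. Setting a baseline for each parameter is ordinary SAP content, and the SAP is to be finalized before database lock and overrides the protocol. No test or decision rests on these tables.

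Much of this stands, and it is why the point is minor. It does not remove the point. The rule is explicit, makes no exception and fails when followed. No text supplied equates Day 1 with baseline, and Section 11.13 points to a different visit. A SAP may already have settled it, but that cannot be seen here.

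Three narrower remarks also deserve weight.

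- The renal monitoring criteria in Sections 11.5 and 11.12.1 do not name Day 1, but where they use a multiple of baseline they leave that term undefined. It can be said only that they do not depend on the wording of Section 12.5.2.
- The summaries are for continuous outcomes, so change may not apply to some categorical urine items.
- A general baseline rule reaches all seven groups. Section 10.2.1 does not mark Day 1 hematology, chemistry or ECG as predose. If one of these were done after the infusion began, its reference would move back to Screening. That is still a proper pre-treatment value, but the reader should know it can happen.

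**Conclusion.** The point holds. As written, Section 12.5.2 gives no echocardiogram change (0 of 2 per patient) and no like-for-like first-morning-void change (0 of 13). Post-dose urine can be computed (3 of 3), but its Day 1 value is not a pre-treatment baseline. The severity is minor: actual values are presented, laboratory abnormalities are listed, the analysis is descriptive, and the needed pre-treatment values are already collected. The conclusion rests on the scheduled visits with full attendance and on the protocol text alone. A baseline definition in the SAP could already have resolved it.

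**What to change.** In Section 12.5.2 or the SAP, replace the Day 1 reference with change from baseline, where baseline is the last non-missing value before the start of the first infusion and, for urinalysis, of the same sample type. In addition:

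- State that this means the Screening echocardiogram and the Pre-Infusion first morning void.
- Do not let a random Screening urine stand in for a missing Pre-Infusion void without a flag.
- Report post-dose urinalysis as its own series, with Day 1 labelled a first-dose reference and not a baseline.
- Use the same baseline in the Section 12.4 tables.
- Record whether each Day 1 hematology, chemistry and ECG value came before the infusion, so that the rule picks the intended value.

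If the SAP already defines baseline this way, it should note the difference from the protocol, as Section 12.1 requires. The cost is one sentence of definition and its programming. No visit, sample or patient is added.
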